4. PATIENT SELECTION

This study can fulfill its objectives only if appropriate patients are enrolled. The following eligibility criteria are designed to select patients for whom protocol treatment is considered

appropriate. All relevant medical and non-medical conditions should be taken into consideration when deciding whether this protocol is suitable for a particular patient.

4.1. Inclusion Criteria

Patient eligibility should be reviewed and documented by an appropriately qualified member of the investigator's study team before patients are included in the study.

Patients must meet all of the following inclusion criteria to be eligible for enrollment into the study:

4.1.1. Monotherapy Cohort

1. Patients with selected advanced hematologic malignancies who are refractory, resistant or intolerant to prior therapies. Eligible patients are limited to 1. Myelodysplastic Syndrome (any MDS International Prognostic Scoring System or IPSS score), 2. Myelofibrosis, 3. Chronic Myelomonocytic Leukemia (CMML), 4. CML T315I mutants, 5. CML in whom the T315I mutation is not present (any phase; must have received at least one prior treatment), 6. Acute Myeloid Leukemia (AML).
2. Patients with CML:
 - a. Must have a confirmed diagnosis as evidenced by the presence of the BCR-ABL translocation [t(9;22)] by fluorescence in situ hybridization (FISH), cytogenetics, or quantitative polymerase chain reaction (QPCR) for chronic myeloid leukemia in either chronic, accelerated or blast phase.
 - b. Non-T315I CML must have received at least one prior therapy.
 - c. May be resistant or intolerant as defined by:
 - In CML-CP, primary resistance is defined as failure to achieve a complete hematologic response (CHR) following 3 months on therapy; failure to achieve any cytogenetic response (CyR) following 6 months on therapy, failure to achieve a major cytogenetic response following 12 months on therapy, or failure to achieve a complete cytogenetic response following 18 months on therapy;
 - Secondary resistance is defined as a loss of CHR (defined by leukocytosis confirmed with at least one WBC>15K not felt to be due to a secondary cause); loss of a MCyR (defined by $\geq 30\%$ increase in the number of metaphases); or disease progression to AP or BP;
 - In CML-AP or CML-BP, resistance is defined as the failure to achieve a hematologic response, an increasing WBC, or an overt disease progression.

- Intolerance for all phases is defined as discontinuation of prior therapy due to adverse events at the lowest approved dose or if a patient can only tolerate prior therapy at less than the lowest approved dose.
 - In addition, for all phases (except patients with T315I mutations), patients are eligible in the case of unsatisfactory clinical response to the initial course of TKI, but who do not meet the definition for refractory, resistant or intolerant (eg, a CML CP patient who rapidly progresses on primary therapy, but does not meet the criteria for primary resistance because they have not been on TKI for 3 months; or patients with co-morbid diseases who cannot tolerate TKI therapy).
 - To be considered in chronic phase, all the following must be met:
 - <15% blasts in peripheral blood and bone marrow;
 - <30% blasts and promyelocytes in peripheral blood or bone marrow;
 - <20% basophils in peripheral blood;
 - Platelets $\geq 100 \times 10^9/L$;
 - No EMD other than spleen or liver.
 - To be considered in accelerated phase, one or more of the following must be met:
 - $\geq 15\%$ blasts in peripheral blood;
 - $\geq 30\%$ blasts + promyelocytes in peripheral blood;
 - $\geq 20\%$ basophils in peripheral blood;
 - Platelet count $\leq 100 \times 10^9/L$ unrelated to therapy;
 - Clonal evolution.
 - To be considered in blast phase, either one of the following criteria must be met:
 - $\geq 30\%$ blasts in peripheral blood or bone marrow, or
 - Extramedullary disease.
3. All anti-cancer treatments should be discontinued as follows:
- Anagrelide should be discontinued 7 days prior to first dose of investigational product;

- Dasatinib should be discontinued from 1 day (24 hrs) prior to first dose of investigational product;
 - Nilotinib should be discontinued from 3 days (72 hrs) prior to first dose of investigational product;
 - Imatinib should be discontinued from 4 days (96 hrs) prior to first dose of investigational product;
 - Bosutinib should be discontinued from 4 days (96 hrs) prior to the first dose of investigational product;
 - Ponatinib should be discontinued from 7 days (168 hrs) prior to the first dose of investigational product;
 - All other anti-cancer treatments should be discontinued ≥ 2 weeks from first dose of investigational product, e.g., chemotherapy (including intrathecal), radiotherapy, cytokines, investigational agents, or hormones.
4. Age ≥ 20 years old.
 5. ECOG performance status of 0, 1, or 2.
 6. Patients who have previously received an autologous stem cell transplant are eligible provided that the transplant occurred more than 30 days prior to study entry and if the patient has recovered from transplant associated toxicities prior to study entry.
 7. Patients with a history of allogeneic stem cell transplant are eligible for study participation provided that the transplant was greater than 60 days prior to first dose of investigational product and the patient has recovered from transplant-associated toxicities prior to first dose of investigational product.
 8. Adequate organ function as defined by the following criteria:
 - Serum aspartate transaminase (AST) and serum alanine transaminase (ALT) ≤ 3 x upper limit of normal (ULN), or AST and ALT ≤ 5 x ULN if liver function abnormalities are due to underlying malignancy;
 - Total serum bilirubin ≤ 2 x ULN (except patients with documented Gilbert's syndrome);
 - Serum creatinine ≤ 1.5 x ULN or estimated creatinine clearance ≥ 60 mL/min as calculated using the method standard for the institution.
 9. Serum/urine pregnancy test (for females of childbearing potential) that is negative at screening and immediately prior to initiation of treatment (first dose).

Male and female patients of childbearing potential must agree to use a highly effective method of contraception throughout the study and for at least 180 days after the last dose of assigned treatment. Female patients are of childbearing potential if, in the opinion of the investigator, she is biologically capable of having children and is sexually active. Female patients with permanent sterilization or post-menopausal are not considered as childbearing potential. (Post-menopausal is defined medically confirmed post-menopausal status defined as spontaneous cessation of regular menses for at least 12 consecutive months with no alternative physiological causes.) Male patients are of childbearing potential if, in the opinion of the investigator, he is biologically capable of having children and is sexually active.

10. Evidence of a personally signed and dated informed consent document indicating that the patient (or legal representative) has been informed of all pertinent aspects of the study.
11. Willingness and ability to comply with the study scheduled visits, treatment plans, laboratory tests and other procedures.

4.1.2. Combination Cohort 1, Expansion Cohort of LDAC combination for efficacy and Combination Cohort 2 (Unfit and Fit Patients)

1. Patients with AML or RAEB-2 High-Risk MDS who are newly diagnosed according to the WHO 2008 Classification and previously untreated. Eligible patients with MDS, as well as eligible patients with AML arising from an antecedent hematologic disease (AHD) or MDS may have had **one** prior regimen with commercially-available agent(s) (eg, azacitidine or decitabine) for the treatment of their prior hematologic disease. The patients may not have had any prior therapy for their AML.
2. AML patients include de-novo AML, AML evolving from MDS or other AHD and AML after previous cytotoxic therapy or radiation (secondary AML).
 - For a diagnosis of AML, a bone marrow blast count of 20% or more is required.
 - For AML defined by cytogenetic aberrations t(8;21), inv(16) or t(16;16) and some cases of erythroleukemia the proportion of bone marrow blasts may be <20%.
 - In AML FAB M6a (erythroid leukemia) $\geq 20\%$ of non-erythroid cells in the bone marrow must be leukemic blasts and $\geq 50\%$ of the cells are erythroid precursors.
 - In AML with monocytic or myelomonocytic differentiation, monoblasts and promonocytes, but not abnormal monocytes, are counted as blast equivalents.
3. For a diagnosis of high-risk Myelodysplastic Syndrome RAEB-2 the patient must have 10-19% bone marrow blasts.
4. Age:
 - ≥ 20 years old for patients enrolled in Combination Cohort 2 (Fit Patients);

- ≥ 55 years old for patients enrolled in Combination Cohort 1 and Expansion Cohort of LDAC combination for efficacy (Unfit Patients).
5. ECOG Performance Status 0, 1, or 2.
 6. Patients with AML or High-Risk MDS who have **one or more** of the criteria below are considered unfit for intensive chemotherapy and are eligible for Combination Cohort 1 and Expansion Cohort of LDAC combination for efficacy (Unfit Patients):
 - Age ≥ 75 years;
 - ECOG Performance Status of 2;
 - Serum creatinine > 1.3 mg/dL;
 - Severe cardiac disease (eg, LVEF $< 45\%$ by multi-gated acquisition [MUGA] or echocardiography [ECHO] at screening).
 7. Patients with AML or high-risk MDS and have **none** of the following criteria are considered fit for intensive chemotherapy and are only eligible for Combination Cohort 2 (Fit Patients):
 - Age ≥ 75 years;
 - ECOG Performance Status of 2;
 - Serum creatinine > 1.3 mg/dL;
 - Severe cardiac disease (eg, LVEF $< 45\%$ by MUGA or ECHO at screening).
 8. Adequate Organ Function as defined by the following:
 - Serum aspartate transaminase (AST) and serum alanine transaminase (ALT) ≤ 3 x upper limit of normal (ULN), or AST and ALT ≤ 5 x ULN if liver function abnormalities are due to underlying malignancy;
 - Total serum bilirubin ≤ 2 x ULN (except patients with documented Gilbert's syndrome);
 - Serum creatinine ≤ 1.5 x ULN or estimated creatinine clearance ≥ 60 mL/min as calculated using the method standard for the institution.
 9. All anti-cancer treatments (unless specified) should be discontinued ≥ 2 weeks from first dose of investigational product, for example: targeted chemotherapy, radiotherapy, investigational agents, hormones, anagrelide or cytokines.

- For control of rapidly progressing leukemia, hydroxyurea or leukopheresis may be used before and for up to 1 week after first dose of PF-04449913;
 - Patients with controlled CNS leukemia (documented by two consecutive assessments of zero blast count in cerebrospinal fluid), and who are still receiving intrathecal (IT) therapy at study entry are considered eligible, and will continue to receive IT therapy.
10. Resolved acute effects of any prior therapy to baseline severity or Grade ≤ 1 CTCAE except for AEs not constituting a safety risk by investigator judgement.
11. Serum/urine pregnancy test (for females of childbearing potential) that is negative at screening and immediately prior to initiation of treatment (first dose).

Male and female patients of childbearing potential must agree to use a highly effective method of contraception throughout the study and for at least 180 days after the last dose of assigned treatment. Female patients are of childbearing potential if, in the opinion of the investigator, she is biologically capable of having children and is sexually active. Female patients with permanent sterilization or post-menopausal are not considered as childbearing potential. (Post-menopausal is defined medically confirmed post-menopausal status defined as spontaneous cessation of regular menses for at least 12 consecutive months with no alternative physiological causes.) Male patients are of childbearing potential if, in the opinion of the investigator, he is biologically capable of having children and is sexually active.

12. Evidence of a personally signed and dated informed consent document indicating that the patient (or legal representative) has been informed of all pertinent aspects of the study.
13. Willingness and ability to comply with the study scheduled visits, treatment plans, laboratory tests and other procedures.

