disease. Clinical benefit (CR + CRi+ PR + PRi+ stable disease + MR) was shown in 16 patients (57.1%), including 7 patients (25%) with stable disease. Among the 2 patients with CML-AP/BC, 1 patient had a partial cytogenetic response. None of the patients with CML-CP had a cytogenetic response. Out of the 46 patients evaluated for efficacy, 2 out of 7 MDS/CMML patients (28.6%), 2 out of 7 MF patients (28.6%) and 9 out of 28 AML patients (32.1%) had an OR. No CML patients had an OR.

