Appendix 9. Response Criteria and Progression Definitions for Chronic Myeloid Leukemia

Hematologic Responses to Treatment; maintained for at least 4-weeks

Subjects with Accelerated or Blast Phase CML	
Hematologic Responses	Definition
Return to Chronic Phase	Disappearance of features defining accelerated & blast phases, but still in chronic phase (May have platelets $<100 \times 10^9/L$, if related to therapy) Persistence of clonal evolution, if present at the time of therapy, is acceptable for return to chronic phase
Minor Response	$<15\%$ blasts in marrow and blood $< 30\%$ blasts + promyelocytes in marrow and same in blood $< 20\%$ basophils in peripheral blood No extramedullary disease other than spleen and liver
No Evidence of Leukemia (NEL)	Blast $\leq 5\%$ in bone marrow $0.5 \times 10^9 \leq ANC < 1.0 \times 10^9/L$ $20 \times 10^9 \leq$ Platelets $< 100 \times 10^9/L$ No blood blasts or promyelocytes $<20\%$ basophils in blood Myelocytes + metamyelocytes $<5\%$ in blood No extramedullary involvement (incl. hepato- or splenomegaly)
Complete Hematologic Response	Blast $\leq 5\%$ in bone marrow No peripheral blasts or promyelocytes Myelocytes + metamyelocytes $<5\%$ in blood $ANC \geq 1.0 \times 10^9/L$ WBC \leq institutional ULN Platelets ≥ 100 but $<450 \times 10^9/L$, unless related to therapy $<20\%$ basophils in blood No extramedullary involvement (incl. hepato- or splenomegaly)
Subjects with Chronic Phase CML	
No Evidence of Leukemia (NEL)	$0.5 \times 10^9 \leq ANC < 1.0 \times 10^9/L$ $20 \times 10^9 \leq$ Platelets $< 100 \times 10^9/L$ No blood blasts or promyelocytes $<20\%$ basophils in blood Myelocytes + metamyelocytes $<5\%$ in blood No extramedullary involvement (incl. hepato- or splenomegaly)
Complete Hematologic Response	No Peripheral blasts or promyelocytes Myelocytes + metamyelocytes $<5\%$ in blood $ANC \geq 1.0 \times 10^9/L$ WBC \leq institutional ULN Platelets ≥ 100 but $<450 \times 10^9/L$, unless related to therapy $<20\%$ basophils in blood No extramedullary involvement (incl. hepato- or splenomegaly)

Cytogenetic Responses to Treatment (Any Phase of CML)

Cytogenetic Responses*	% Philadelphia chromosome positive cells
None	> 95%
Minimal	66-95%
Minor	36-65%
Partial	1-35%
Complete	0%
Major	Complete + Partial Rates

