Appendix 5. Response Criteria for Chronic Myeloid Leukemia

Objective response and Disease Progression

The objective status at each visit is determined per investigator evaluation (see Protocol Appendix 9). However, the status will be verified per clinical judgment by the Sponsor. Reporting will be done for subjects in chronic phase and accelerated phase/blast crisis at baseline separately. The following categories on the CRF page will be considered objective response and disease progression respectively for the purpose of this study. A response needs to be confirmed by a subsequent investigator assessment a minimum of 4 weeks later. Subjects whose response is not confirmed will be deemed as un-confirmed responders.

Accelerated Phase/Blast Crisis (AP/BC)

Objective Response (hematologic)

Disease assessments

- Complete hematologic response (CHR);
- No evidence of leukemia (NEL);
- Return to chronic phase;
- Minor response.

Disease Progression

- Progressor to Accelerated Phase or Blast Crisis from Chronic Phase or Return to Chronic Phase;
- Progressor from Accelerated Phase to Blast Crisis;
- Loss of confirmed CHR;
- Loss of major cytogenetic response.

Chronic Phase

Objective Response

Disease status assessments

- Complete hematologic response (CHR);
- No Evidence of Leukemia (NEL).

Disease Progression

- Early progressor from Chronic Phase;
- Progressor to Accelerated Phase or Blast Crisis from Chronic Phase or Return to Chronic Phase;
- Loss of confirmed CHR;
- Loss of major cytogenetic response.

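### SAP Appendix 5 does not require a CML objective response to be absent at baseline, so some eligible patients can meet it at entry and be listed as confirmed responders with unchanged disease

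*Protocol*

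**What the plan says.** **Entry (Protocol 4.1.1, criterion 2).** Primary resistance in chronic phase can be a missed hematologic milestone at 3 months or a missed cytogenetic milestone at 6, 12 or 18 months. The last of these is "failure to achieve a complete cytogenetic response following 18 months on therapy". Intolerance is a separate route in every phase.

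**Phase (same criterion).** The chronic-phase rule begins "To be considered in chronic phase, all the following must be met". It sets upper limits on blasts, promyelocytes and basophils, requires platelets of at least 100 x10^9/L, and allows no extramedullary disease outside spleen or liver. The accelerated-phase rule begins "To be considered in accelerated phase, one or more of the following must be met". Its list includes platelets at or below 100 x10^9/L unrelated to therapy, and clonal evolution.

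**Response (Protocol Appendix 9).** CHR and Minor Response describe the patient's state at a visit. Minor Response has four conditions: blasts below 15%, blasts plus promyelocytes below 30%, basophils below 20%, and "No extramedullary disease other than spleen and liver". For return to chronic phase, the appendix adds: "Persistence of clonal evolution, if present at the time of therapy, is acceptable for return to chronic phase".

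**Classification (SAP Appendix 5 and Section 6.1).** In chronic phase, CHR and no evidence of leukemia (NEL) count as objective response. In accelerated or blast phase, CHR, NEL, return to chronic phase and Minor Response count. The confirmation rule is "A response needs to be confirmed by a subsequent investigator assessment a minimum of 4 weeks later". Section 6.1 dates the response to the first documented one. Neither place mentions status at baseline.

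**Output.** For the monotherapy cohort, SAP 8.2.2 provides listings of disease status only. Protocol 9.3 adds the date of first response to those listings.

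**The concern.** The entry rules and the response definitions do not exclude each other. A patient can satisfy both on the day of the lead-in dose, and no rule ties a CML response to a change from baseline. The 4-week confirmation does not help, because disease that stays the same passes it.

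At stake is the meaning of the objective response label for CML patients. This cohort has a secondary objective of preliminary evidence of efficacy, and with few patients each listed response carries weight. A reader of the listing would take a confirmed response with a date as something that happened on treatment.

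**Working it through.** The plan states no figure on this point, so there is none to reproduce. The check sets the three sets of rules side by side and runs example patients through them. Platelets are in x10^9/L. Values not mentioned are unremarkable.

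| Patient at entry | Phase (4.1.1) | Possible entry route | Category already met (Appendix 9) | Objective response if unchanged |
|---|---|---|---|---|
| 1. 20 months on a TKI, 30% Ph+ cells, normal counts, no organomegaly | Chronic | No complete cytogenetic response at 18 months | CHR | Yes |
| 2. Platelets 90, unrelated to therapy | Accelerated | Intolerance | Minor Response | Yes |
| 3. Clonal evolution, normal counts | Accelerated | Intolerance | Minor Response, CHR | Yes |
| 4. Clonal evolution, WBC 3 x ULN, blasts 8% in blood and 10% in marrow | Accelerated | Increasing WBC | Minor Response | Yes |
| 5. Blood blasts 18% | Accelerated | Any | None | No |
| 6. Basophils 22% | Accelerated | Any | None | No |
| 7. Blasts 35% | Blast | Any | None | No |

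**Chronic phase.** Patient 1 shows the route in the quoted criterion. The three cytogenetic milestones and intolerance do not require CHR to be lost or never reached, and the phase rule does not exclude it. Criterion 3 stops TKIs only 1 to 7 days before the first dose. NEL cannot be met at entry in chronic phase, because it needs platelets below 100 and the phase rule needs at least 100.

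**Accelerated phase.** Minor Response has no platelet, WBC or clonal condition, so patients 2 to 4 meet it. Because clonal evolution may persist, patient 3 can also be read as meeting return to chronic phase at entry. Resistance in this phase means failure to achieve a hematologic response, an increasing WBC or overt progression. A patient already in Minor Response does not fit the first of these, so entry must come by another route: one of the other two, intolerance, or an unsatisfactory response to the initial TKI course.

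**Stable versus improving.** If patient 1 stays at 30% Ph+ cells, the listing shows an objective response through CHR. If patient 1 goes from 30% to 0%, it shows the same response through the same CHR.

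**Size.** Study B1371001 had 5 CML patients among 47 (Protocol 1.2.8.1.1). Assuming the same share here:

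- expected CML patients among 15: 15 x 5/47 = 1.6
- chance of at least one: 1 - (42/47)^15 = 0.81

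These figures count any CML patient. The documents do not give the fraction f of CML patients who already meet a category at entry. The expected number affected is 1.6 x f, which runs from 0 (f = 0) to 1.6 (f = 1).

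**The case against.** **The Sponsor checks status.** SAP Appendix 5 says the Sponsor will verify the investigator's status using clinical judgement. This could catch some cases. It states no baseline rule, so it does not settle how patients 1 to 4 are classified.

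**Nothing is estimated from it.** This stands. The cohort's primary endpoint is safety and DLTs, and its efficacy output is listings. The SAP also lists cytogenetics (8.2.10.5), CML transcripts with change from baseline (8.2.10.8), prior therapy response (8.2.10.3), and spleen and liver change (8.2.10.7). A careful reader could reconstruct what happened. The response label and its date would still be misleading.

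**Cytogenetic response is left out on purpose.** A reader might infer that SAP Appendix 5 turns a patient who gains a cytogenetic response into a non-responder. That does not hold for the patient in the quoted criterion who is in CHR, because CHR gives the label either way. It can hold for others: a chronic-phase patient going from 100% to 0% Ph+ cells with a palpable spleen fails CHR and is not a response. However, the accelerated/blast list is headed as hematologic and cytogenetics are listed separately, so a hematologic definition is a legitimate choice. The MDS and MF appendices do count cytogenetic response, but CML need not match them.

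**B1371001 shows the problem.** A reader might infer this from one of two accelerated/blast patients having a partial cytogenetic response although "No CML patients had an OR". The documents do not give that study's definition of objective response, so the result supports neither side. If the definition was the same, it would also mean that no CML patient there was credited with a response present at baseline.

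**Conclusion.** The concern holds as a gap in the classification rule. Under Protocol 4.1.1, two groups can meet a CML objective response category at entry: chronic-phase patients in CHR who are resistant only by cytogenetic milestone or are intolerant, and accelerated-phase patients classified only by platelets or clonal evolution who enter other than by failure to achieve a hematologic response. If their disease does not change, SAP Appendix 5 and Section 6.1 list a confirmed response dated to the first assessment.

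The consequence is small. It concerns a secondary endpoint, listings only, in at most 15 patients across several malignancies, and the number affected is unknown. It would be wrong to infer that every CML patient starts in response: accelerated phase by blood blasts or basophils, and blast phase by blast count, do not meet a category at entry. Nor are 1.6 patients and 81% figures for affected patients. They describe any CML enrolment, at a case mix assumed from B1371001.

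**What to change.** 1. In SAP Appendix 5 and Section 6.1, count a CML hematologic category as objective response only if the baseline assessment did not already meet that category or better.
2. In the CML listing, flag patients in response at baseline and show their baseline category separately.
3. State how a patient is shown when baseline status cannot be determined, since Protocol Table 1 lets the screening marrow be waived with Sponsor approval.
4. Label the current CML objective response as hematologic for both phases. Only the accelerated/blast list says so now. Adding cytogenetic response to the list is optional.

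The cost is SAP wording and one derived flag. Table 1 already schedules blood counts with differential, spleen and liver size, marrow and cytogenetics before treatment. The laboratory list in Protocol 7.1.3 does not name the immature-cell counts that CHR needs, so the baseline category is best taken from the investigator's own classification, as at later visits. The drawback is that the listed number of responses may fall.
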